4.1 Description of Study Design

This is a pilot, proof of concept, placebo-controlled, parallel study. Participants will be recruited from NYU Langone Medical Center's ENT Department and will receive either high-dose intranasal oxytocin or the placebo, a nasal spray containing the same inactive ingredients as the active drug: magnesium chloride crystals, citric acid anhydrous gran., sodium citrate powder, sterile water for irrigation, and Pcca Mucolox liquid base to replicate the feel and consistency of the oxytocin nasal spray. When changing the compounding pharmacy, we conducted a blinded test of placebo formulations. We found that the placebo containing all of the inactive ingredients as the active oxytocin nasal spray was a significantly better match in consistency to the active drug, as compared to distilled water and Pcca Mucolox. The primary outcome measure for this study will be a greater than 50% improvement in tinnitus loudness on the Visual Analog Scale (VAS). The secondary outcome measure will be improvement (p < 0.10) in the Tinnitus Handicap Inventory Severity Scale (THI)/Clinical Global Impression Scale (CGI) and Tinnitus Functional Index (TFI) (26, 27, 28). The metrics on the secondary endpoints are exploratory only and as such we will not look for specific changes. These results will guide us in the next, larger study.

The study will consist of 3 phases:

- 1. A 1 week baseline phase during which time we will track daily tinnitus loudness on VAS using a study log. Patients will not receive any study drug during this phase. No changes in any concomitant medications will be allowed during this phase. In addition, the use of dinoprostone or ephedrine is not permitted throughout the study.
- 2. A 9 week non-blinded phase is which all patients will receive the oxytocin nasal spray 4 times daily. All patients will begin at a dose of 30 IU 4 times daily for 2 weeks; If no response is reported (defined as a decrease in VAS of < 2), they will have the dose increase by 5 IU per spray every 2 weeks, until a maximum dose of 45 IU 4 times daily. If patients report improvement (defined as improvement in VAS >3) at any dose, they will remain at that dose through the end of the second phase. In the event that the patient experiences a moderate side effect, the dose will be decreased to the previous dose for the remainder of this phase.
- 3. A 6 week double-blinded phase in which half of the participants will receive oxytocin nasal spray and half will receive placebo nasal spray. Neither the PI nor subject will know which drug they are receiving. However, the study coordinator will have access to this information as required to assign the medications.

Patients will come to the Preston Robert Tisch Center for Men's Health for study visits every 2 weeks and be administered the VAS and THI/CGI scales by the research coordinator or principal investigator. The screening visit will be the most comprehensive and include obtaining informed consent, a physical exam with vital signs, laboratory studies, questionnaires, an ECG, and review of medical and medication history to confirm all inclusion criteria are met and that there are no exclusion criteria present. During these visits they will have urine testing for sodium and osmolality. Every other week, they will receive a phone call from study staff to discuss their experience using the study drug and monitor for any adverse effects. They will complete the Tinnitus Functional Index questionnaire over the phone as well. When the subjects come in for their study visit, 4 weeks after the baseline period, they will receive enough study medication for the rest of the study, to allow for randomization to placebo or active drug at that time.

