Reference Therapy	The investigational product will be compared to placebo, a nasal spray consisting of magnesium, chloride crystals, citric acid anhydrous gran., sodium citrate powder, sterile water for irrigation, and Pcca Mucolox liquid base.
Key Procedures	Oxytocin (or placebo) will be self – administered by the study participants daily. Study visits will occur every two weeks, from prior to the baseline week to 15 weeks after baseline, during which patients will be asked to rate the loudness of their tinnitus (VAS scale) and complete the THI questionnaire. Additional questionnaires and urinalysis will be performed at every study visit to monitor sodium levels and osmolality.
Statistical Analysis	The primary analysis is to provide an estimate of the partial eta squared effect size difference between placebo and treatment during the blinded phase of the study as well as to provide initial efficacy, safety and tolerability estimates during the initial open label study phase.

Schematic of Study Design

1 Key Roles

Primary investigator: [name] NYU Langone Medical Center [name] [name] [contact]

Sub-investigator (Headache Fellow): [name], MDNYU Langone Medical Center [name] [name] [contact]

Research Coordinator, Regulatory Specialist, Data Management, and Primary Contact: [name] NYU Langone Medical Center [name] [name] [contact]

2 Introduction, Background Information and Scientific Rationale

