6.1.2 Formulation, Appearance, Packaging, and Labeling

This nasal spray will be a liquid prepared at VLS Pharmacy/New Drug Loft and contained in 30mL amber glass bottles with nasal sprayers. Both active drug and the placebo will appear identical in the glass bottles. These bottles will be labeled with subject specific labels to be marked by the study coordinator. The label will also say "Oxytocin/Placebo." This study medication is investigational and will be formulated specifically for the purpose of meeting the trial plan.

6.1.3 **Product Storage and Stability**

Study agent and placebo will be stored in amber glass bottles in a secure refrigerator that only study personnel will have access to. The medications will be kept between 36°F to 46°F (2°C - 8°C). They cannot be frozen or exposed to direct light. After its preparation, the study agent is good for 30 days in the refrigerator. It must be kept out of the reach of children.

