6.2 Study Agent Accountability Procedures

After the compounding pharmacy prepares and delivers the active drug and placebo, the study coordinator will have access to the secure refrigerator where study drug is stored. At Visits 3, 5, 7, and 9, she will distribute the study agent (oxytocin nasal spray) to each participant. The participants will receive only enough of the study agent for the next 2 weeks of the study. They will have to return to the office at weeks 11 and 13 to receive study drug or placebo for the double blind phase of the study.

Regular study drug reconciliation will be performed to document drug assigned, drug consumed, and drug remaining. This reconciliation will be logged on a drug accountability log, and signed and dated by the study team.

Subjects will receive a phone call from the study coordinator to discuss the subject's experience using the study drug the prior week. Subjects will also have to complete a daily log noting the severity of their tinnitus for that day and the time they took their medication. Study staff will review this information at each visit, every other week.

7 Study Procedures and Schedule

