7.1 Study Procedures/Evaluations

Patients will come to the Preston Robert Tisch Center for Men's Health for study visits every 2 weeks and be administered the VAS and THI/CGI scales by the research coordinator or principal investigator. The screening visit will be the most comprehensive and include obtaining informed consent, a physical exam with vital signs, laboratory studies, questionnaires, an ECG, and review of medical and medication history

to confirm all inclusion criteria are met and that there are no exclusion criteria present. During these visits they will have urine testing for sodium and osmolality. Every other week, they will receive a phone call from study staff to discuss their experience using the study drug and monitor for any adverse effects. They will complete the Tinnitus Functional Index questionnaire over the phone as well. When the subjects come in for their study visit, 4 weeks after the baseline period, they will receive enough study medication for the rest of the study, to allow for randomization to placebo or active drug at that time.

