9.6 Measures to Minimize Bias

9.6.1.1 Enrollment/Randomization/Masking Procedures

After receiving intranasal oxytocin for 9 weeks, participants will be randomized to either intranasal oxytocin or placebo. The fellow will use a random number generator to assign subjects to 0 (placebo) or 1 (active drug) each time a subject enters the randomized phase of the study. He will use block randomization so that treatment group assignments are balanced. This information will be created and stored in the Randomization Log. This will be kept securely, stored in a separate Randomization binder to ensure the non-blinded fellow only accesses the information as needed to randomize the study medication at visit 11.

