15.1 Study Leadership

The Study Team will govern the conduct of the study. The Study Team will be composed of the PI, Medical Fellow, and Research Coordinator.

16 Conflict of Interest Policy

The independence of this study from any actual or perceived influence, such as by the pharmaceutical industry, is critical. Therefore any actual conflict of interest of persons who have a role in the design, conduct, analysis, publication, or any aspect of this trial will be disclosed and managed. Furthermore, persons who have a perceived conflict of interest will be required to have such conflicts managed in a way that is appropriate to their participation in the trial. The study has established policies and procedures for all study group members to disclose all conflicts of interest and will establish a mechanism for the management of all reported dualities of interest.

Any investigator who has a conflict of interest with this study (patent ownership, royalties, or financial gain greater than the minimum allowable by their institution, etc.) must have the conflict reviewed by the NYU Langone Conflict of Interest Management Unit (CIMU) with a Committee-sanctioned conflict management plan that has been reviewed and approved by the study sponsor prior to participation in this study. All NYULMC investigators will follow the applicable conflict of interest policies.

17 References

- 1. Bhatt SM Bhatt JM, Lin HW, Bhattacharyya N. Prevalence, Severity, Exposures, and Treatment Patterns of Tinnitus in the United States. JAMA Otolaryngol Head Neck Surg. 2016 Oct 1;142(10):959-965.
- Moller AR. Sensorineural Tinnitus: Its Pathology and Probable Therapies. Int J Otolaryngol. 2016;2016:2830157. doi: 10.1155/2016/2830157. Epub 2016 Feb 8. Review. PubMed PMID: 26977153; PubMed Central PMCID: PMC4761664.

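### The plan permits a coordinator with access to treatment assignments to collect subjective outcomes in the blinded phase, and leaves the VAS source and week-3 baseline of the primary AUC unstated

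*Combined protocol and SAP*

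**What the plan says.** **Access to assignments.** Section 4.1 describes a double-blind phase in which the PI and the participant are unaware of the arm, and continues: "However, the study coordinator will have access to this information as required to assign the medications". Section 9.6.1.1 gives randomisation to the fellow and keeps the log in a separate binder "to ensure the non-blinded fellow only accesses the information as needed to randomize the study medication at visit 11". It does not mention the coordinator.

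**Outcome collection.** Sections 4.1 and 7.1 say that at the two-weekly office visits participants will "be administered the VAS and THI/CGI scales by the research coordinator or principal investigator". On the alternate-week phone contacts, "They will complete the Tinnitus Functional Index questionnaire over the phone as well". Section 6.2 says who calls: "Subjects will receive a phone call from the study coordinator".

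**How many coordinators.** Section 1 has one entry, "Research Coordinator, Regulatory Specialist, Data Management, and Primary Contact". Section 15.1 says: "The Study Team will be composed of the PI, Medical Fellow, and Research Coordinator".

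**Handling of bottles.** Section 6.1.2 says: "These bottles will be labeled with subject specific labels to be marked by the study coordinator". The same section has active and placebo bottles looking identical, under a label that carries both names.

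**Primary endpoint.** Sections 4.2.1.1, 9.2, 9.4 and 9.4.2 define a trapezoidal area under the VAS curve from week 3 to week 6 of the blinded phase, after subtracting the week-3 value. The first two weeks are set aside as washout. None of these sections says whether the VAS comes from the daily log (6.1.10) or from a reading taken at a visit.

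**The concern.** Every efficacy measure here is subjective, and the six-week blinded phase is the only randomised comparison. Sections 9.2 and 9.4.2 themselves warn that knowledge of treatment can bias the open-label results. If the person who administers a scale knows the arm, scoring or prompting can differ between arms. Section 9.6.1.2 marks evaluation of blinding as not applicable, so the plan has no means of noticing a leak.

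The measures are not equally exposed. CGI-I is the clearest case, although the documents do not say who scores it. THI and TFI are answered by the participant, so only prompting is at issue. A VAS log that the participant completes at home is hardly exposed. Whether the primary endpoint has that protection depends on its source, and the plan does not state the source.

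**Working it through.** The plan gives no figure on this point to reproduce. The check is a comparison of sections and a visit calendar.

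**1. One role or two.** The documents use both study coordinator and research coordinator and never equate them. Section 1 lists one coordinator, and the team in 15.1 has one. The natural reading is a single role. This is an inference.

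**2. Who may know the arm.** Section 4.1 names the coordinator and 9.6.1.1 names the fellow. Section 9.6.1.1 does not say that the fellow is the only one, so both can be literally true. In that case two people have routine access, and one of them may administer outcome scales. Separately, 8.6 supplies unblinded assignments after a serious adverse event to two physicians, in context apparently the PI and the independent monitor, and 9.6.1.3 lets the PI break the blind in defined cases.

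**3. Calendar.** Randomisation is at Visit 11, study week 9 (7.2.3.9), so blinded week = study week − 9. The scales are those in the visit checklists (7.2.3.10 to 7.2.4).

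| Visit | Study week | Blinded week | Type | Listed scales |
|---|---|---|---|---|
| 12 | 10 | 1 | phone | TFI |
| 13 | 11 | 2 | office | THI, CGI-I |
| 14 | 12 | 3 | phone | TFI |
| 15 | 13 | 4 | office | THI, CGI-I |
| 16 | 14 | 5 | phone | TFI |
| 17 | 15 | 6 | office | THI, CGI-I |

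The office checklists also list review of the VAS log. Six visits follow randomisation. Section 9.4 excludes the first two blinded weeks, which removes Visits 12 and 13: 6 − 2 = 4. The analysed opportunities are THI and CGI-I at Visits 15 and 17, and TFI at Visits 14 and 16. The text does not exclude the coordinator from any of them. These are opportunities, not measured exposure.

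**4. The week-3 baseline.** Blinded week 3 is study week 3 + 9 = 12, which is Visit 14. The version 1.7 entry in the version history also ties passing the washout to Week 12, Visit 14. That is a phone visit whose checklist lists only the TFI. VAS readings taken at office visits would fall at blinded weeks 2, 4 and 6, with none at week 3. The daily log would cover week 3.

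**5. The same window for the other scales.** THI change (4.2.1.2, 9.2) and CGI and TFI change (9.4.7.6) also run from week 3 to week 6. THI and CGI-I are listed at weeks 2, 4 and 6, so they have no week-3 value. TFI is listed at weeks 1, 3 and 5, so it has no week-6 value.

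**6. Effect of the VAS source on the area.** As an illustration, assume that VAS changes in a straight line by b points per week. The area above baseline is then b × (length)² / 2.
- Log, weeks 3 to 6: b × 3² / 2 = 4.5b
- Office readings, Visit 13 as baseline, weeks 2 to 6: b × 4² / 2 = 8.0b
- Office readings, Visit 15 as baseline, weeks 4 to 6: b × 2² / 2 = 2.0b

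The reported means and standard deviations would differ. A common rescaling of all areas leaves partial eta squared unchanged, so these figures alone do not show that the effect size would move. It could move through different noise and weighting, which the documents do not allow us to quantify.

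**The case against.** Four arguments against the point have weight.

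- **Access is limited and assessment is optional.** The coordinator's access is only what assigning medication needs, and the PI may administer the scales instead. This stands as a limit: the plan permits unblinded assessment and does not require it. Nothing keeps the two tasks apart, however.
- **The primary endpoint is barely touched.** CGI and TFI are exploratory (Section 3, 9.4.7.6), THI is summarised as frequencies by arm, and the blinded-phase checklists point to the log for VAS. This largely stands. A reader might infer that the primary VAS is compromised, or that bottle labelling reveals the arm. The documents support neither.
- **The 4.1 sentence may be outdated.** The same part of 4.1, repeated in 7.1, places the supply for randomisation four weeks after baseline, which does not match randomisation at Visit 11. The coordinator sentence could be another remnant. That is possible, but it is current text and has to be reconciled either way.
- **Week 3 could mean Visit 13.** Two weeks after Visit 11 is Visit 13, an office visit, and the schedules mark unnamed questionnaires at every visit. So a reader should not infer that no week-3 VAS can exist. The version history favours Visit 14, and the log could supply a value on either reading. What stands is that the plan does not choose.

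A reader might also infer that 4.1 and 9.6.1.1 flatly contradict each other. They do not, because 9.6.1.1 never says that nobody else is non-blinded.

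**Conclusion.** The point holds in a limited form and should be fixed. As written, the plan allows someone with access to assignments to collect subjective outcomes in the only randomised comparison, at up to four analysed visits per participant. The documents give neither the size nor the direction of any bias, and they do not show that unblinded assessment will occur. The conclusion assumes that the two coordinator titles are one role, which is likely but not stated, and that the analysed window starts at blinded week 3. If Visit 13 were taken as baseline, its THI and CGI-I would be a further opportunity.

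The unstated VAS source and baseline value are a secondary gap, closer to missing detail than to error, because the log is probably what is meant. It still needs closing: 9.4 leaves room to refine the analyses as data lock approaches, and 9.4.2 judges success on the resulting effect size.

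**What to change.** 1. **Blinding roles.** State identically in 4.1, 6.1.2, 6.2, 7.1 and 9.6.1.1 that from Visit 11 only the fellow accesses assignments and prepares coded bottles, and that the fellow does no outcome assessment. The coordinator and PI remain blinded, hand over the coded bottles and administer the scales. Cross-reference the unblinding provisions in 8.6 and 9.6.1.3 as the exceptions. Delete the sentence in 4.1 that gives the coordinator access.
2. **VAS source.** State in 4.2.1.1, 9.2, 9.4 and 9.4.2 that the participant's daily log is the source. Define the week-3 baseline and the later trapezoid points. One workable choice is the mean of the week-3 entries, followed by weekly means for weeks 4, 5 and 6. Say how an empty week-3 log is handled, because the LOCF rule in 9.4 covers only post-baseline data.
3. **Other scales.** Reconcile the week-3 to week-6 window for THI, CGI and TFI with the weeks at which each is listed.

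**Cost.** These are text edits and a reassignment of tasks among existing staff, with no added visits or participants. The fellow must prepare bottles for the Visit 11, 13 and 15 dispensings. They may not all be ready at Visit 11, because 6.1.3 gives the agent 30 days and the blinded phase lasts 6 × 7 = 42. If weekly means are chosen, within-week detail is lost.

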4.2 Study Endpoints

4.2.1.1 Primary Study Endpoints

The primary outcome measurement will be the collective area under the Visual Analog Scale (VAS) curve above the week 3 baseline as assessed from week 3 to week 6 of the double blinded study phase.

4.2.1.2 Secondary and Exploratory Study Endpoints

Secondary endpoints will consist of safety and tolerability metrics including adverse event incidence and severity, regimen adherence and voluntary study drop-out rates reported during the non-blinded and blinded study phases. The frequency and percentage of each secondary measure will be determined for the non-blinded study phase and by study arm for blinded study phase. Additionally, any changes in THI greater than 1 grade will be determined from week 3 to week 6 of the double blinded study phase. The frequency and percentage of these changes will be summarized by study arm.

A descriptive summary using means and standard deviations stratified by dosage group for the treatment subgroup during the blinded study phase will be performed. The partial eta squared effect size difference will be estimated.

5 Study Enrollment and Withdrawal

Patients older than 18 years old are able to participate. The maximum age of participants is 75 years old. The racial and ethnic origin will reflect the demographics of the populations that seek evaluation of tinnitus at NYU Langone Medical Center.

5.1 Inclusion Criteria

In order to be eligible to participate in this study, an individual must meet all of the following criteria:

- 1. Age ≥18 years
- 2. Continuous perception of subjective tinnitus for \geq 6 months duration
- 3. Evidence of a normal otolaryngologic evaluation within the past year with no evidence of otitis media or externa
- 4. THI of > 16
- 5. Tinnitus loudness rating of >4/10

5.2 Exclusion Criteria

An individual who meets any of the following criteria will be excluded from participation in this study:

- 1. Treated for tinnitus < 6 months due to the acute nature of their condition and slight handicap according to the Tinnitus Handicap Inventory Severity Scale.
- 2. Tinnitus of a muscular or vascular etiology
- 3. Conductive hearing loss
- 4. History of migraine
- 5. History of pulmonary edema
- 6. History of congestive heart failure
- 7. History of severe renal disease
- 8. Prior use of oxytocin nasal spray
- 9. Latex allergy
- 10. Women who are currently breastfeeding
- 11. Pregnancy

Because tinnitus may be co-morbid with migraine, and because migraine may be responsive to treatment with intranasal oxytocin, patients who suffer from migraines will be ineligible to participate. As patients who are allergic to latex may react to the oxytocin spray, individuals with this allergy will be ineligible to participate in the study.

5.3 Vulnerable Subjects

Prisoner-patients will not be approached for participation due to federal and state requirements governing participation of prisoners in research. Pregnant women and individuals with impaired decision-making capacity also will not be approached for this study.

5.4 Strategies for Recruitment and Retention

We will recruit patients from NYU Langone Medical Center's Departments of Otolaryngology and Neurology. We will aim to recruit and enroll 50 patients with a goal of 30 study participants remaining after accounting for some screen failures. Subjects will be identified for study inclusion through otolaryngologists' and neurologists' referrals of patients with tinnitus.

An IRB-approved dear provider letter will be sent to providers from NYU Departments of Otolaryngology and Neurology to assist in identifying potential study participants for referral to the study team. A member of the study team will contact the individual for screening for the study. Data including patient initials, age, date of birth, menstrual status (if applicable), allergies, prior history of migraine, tinnitus quality, severity, duration, ENT evaluation, and current medications will be used for subject identification, informing subjects, and initial discussion of subject eligibility. Information will be obtained through review of medical records and direct interview. The Principal Investigator will review the informed consent form with the potential participant. The Principal Investigator and Research Coordinator will have access to identifiable information as needed for recruitment of study participants. Emails will be securely sent to potential participants via send safe.

